2.3 Post-Treatment Follow-Up Visit Activities

This section presents a list of activities performed at the PTFU Month 1 visit.

Activities are grouped by category (Interview, Exam, etc.). Further information about the activities is presented in Section 3.

POST-TREATMENT
FOLLOW-UP MONTH 1

(30 Days Post last day of study drug) (On-Site):

 INTERVIEW	
 • AE assessment • Prior/concomitant therapy
 EXAM	
 • Contraception counseling • Vital signs
 LAB	
 • Urine pregnancy test (if positive, perform a serum pregnancy test)
 CENTRAL LAB	
 • Pharmacodynamic sample (serum estradiol) • Liver function tests • Lipid panel

UNSCHEDULED VISIT (UNSCH) (On-Site):

 INTERVIEW	
 • AE assessment • Prior/concomitant therapy
---	--

NOTES: In the event an Unscheduled Visit is necessary during the Post-Treatment Follow-up Period, the site will perform at minimum, an assessment of adverse events and concomitant medications. Unscheduled visits should be limited to when a subject is required to return to the office or off-site facility to repeat a procedure or to conduct a procedure to assess safety and the visit is not occurring at the same time when other study related-procedures are scheduled to occur. Clinical judgment should dictate when other safety assessments (such as vital signs and/or symptom-directed physical examination) should be conducted and should also support the reason for the unscheduled visit.

PD VISIT (Site Visit):

 INTERVIEW	
 • AE assessment • Prior/concomitant therapy
---	--

3 STUDY PROCEDURES

3.1 Subject Information and Informed Consent

The investigator or his/her representative will explain the nature of the study to the subject and answer all questions regarding this study. Prior to any study-related screening procedures being performed on the subject or any medications being discontinued by the subject in order to participate in this study, the informed consent statement will be reviewed, signed, and dated by the subject or their legally authorized representative, the person who administered the informed consent, and any other

signatories according to local requirements. A copy of the signed informed consent will be given to the subject and the original will be placed in the subject's medical record. An entry must also be made in the subject's dated source documents to confirm that informed consent was obtained prior to any study-related procedures and that the subject received a signed copy.

Optional biomarker research samples will only be collected if the subject has voluntarily signed and dated a written consent form describing the exploratory research. The written consent may be part of the main consent form. If the subject does not consent to providing optional samples, the subject will still be allowed to participate in the study.

Information regarding benefits for subjects and information regarding provisions for treating and/or compensating subjects who are harmed as a consequence of participation in the study can be found in the informed consent form.

3.2 Eligibility Criteria

Each investigator will employ their clinical judgment in conjunction with protocol-specified eligibility criteria to determine if a subject is eligible for the study. If further clarification is required, questions should be directed to the AbbVie Therapeutic Area Medical Director (TA MD) listed in Section 1.

3.3 Medical History

A complete medical history, including documentation of any clinically significant medical conditions and medications, history of tobacco and alcohol use, and drug abuse will be collected during the Washout Period (if applicable) or during the Screening Period for those subjects who do not require washout. The medical history will be reviewed and should be updated if significant clinical findings are noted on Day 1 prior to dosing and will serve as the Baseline for clinical assessment.

3.4 Gynecological/Obstetrical and Uterine Fibroid History

A detailed gynecological/obstetrical and uterine fibroid history will be collected either during the Washout Period (if applicable) or during the Screening Period for those who do not require washout and will include the following:

- History of uterine fibroids, including year of diagnosis and uterine fibroid symptoms
- History of endometriosis, ovarian cysts, endometrial polyps, or other relevant gynecological conditions
- History of gynecological surgeries and gynecological diagnostic procedures
- History of bleeding, including average cycle length and average number of days with bleeding/cycle over the last 6 months and typical intensity of menstrual periods
- History of irregular bleeding or prolonged bleeding
- Prior hormonal medications, including those taken for treatment of uterine fibroids or other gynecological conditions

- Prior use of nonhormonal medications for the treatment of uterine fibroids and dates of use for 6 months prior to either Washout (if applicable) or Screening
- History of sexually transmitted infections
- Obstetrical history
- Pregnancy history including:
 - Total number of pregnancies
 - Number of live births
 - Number of abortions (including elective, therapeutic, and spontaneous abortions)
 - Delivery outcomes (specifically anomalies, including congenital malformations and chromosomal abnormalities)

The gynecological/obstetrical and uterine fibroid history will be reviewed and should be updated if needed prior to dosing on Day 1 (randomization) and will serve as the Baseline for clinical assessment.

3.5 Adverse Event Assessment

Please refer to Section 6 of the study protocol.

3.6 Prior and Concomitant Therapy

Prior and concomitant medications will be assessed at the time points specified in Section 2 and as described in the protocol.

3.7 Patient-Reported Outcomes and Rating Scales

Prior to the start of the study, AbbVie and/or its designee will provide detailed instructions and training for study site staff administering these scales. The objective of this training is to establish uniformity across sites in administration of these rating instruments. The subjects and/or the investigator or site staff will complete the following questionnaires as appropriate at the time points indicated in Section 2; the questionnaires should be administered before any other study procedures are performed at that visit. Subjects and site staff will be asked to record their responses electronically (which will then be entered into the electronic case report form (eCRF), as applicable).

In the event that a subject or study personnel cannot come to the site because of the COVID-19 pandemic, patient-reported outcome entries may be administered by site staff over the phone and responses collected on paper (source) and transcribed into EDC or entered by site staff directly into an electronic system. AbbVie should be notified.

Uterine Fibroid Symptoms Quality of Life (UFS-QoL) (4-Week Recall)

The UFS-QoL¹ is a disease-specific self-administered questionnaire used to measure health-related quality of life in women with symptomatic uterine fibroids. At the times specified in Section 2, each

subject will be asked to complete a modified (4-week recall) UFS-QoL Questionnaire to report fibroid-related symptoms experienced during the previous 4 weeks.

Reason for Study Participation Questionnaire

In order to better understand the reason why a study participant has decided to enroll in this study, subjects will complete the single-question Reason for Study Participation Questionnaire at the Day 1 Visit (Appendix A of the Operations Manual).

Physician Surgery Questionnaire (PSQ)

Each physician will be asked to complete the PSQ to evaluate the likelihood that the physician would consider surgery or a surgical procedure as one of the treatment options related to uterine fibroids for the subject (Appendix B of the Operations Manual).

Uterine Bleeding Questionnaire (UBQ)

Subjects who did not return a sanitary product collection keg (for alkaline hematin menstrual blood loss analysis) at applicable on-site visits (scheduled on-site visit, Product Collection Visit, Unscheduled, or the PD visit) during the study will be asked to indicate whether they had any uterine bleeding or spotting since their last study visit. If the subject did not have uterine bleeding or spotting the site staff will indicate "No" on the UBQ. If the subject did have bleeding or spotting, the subject will be asked the reason why they did not return sanitary product collection keg at the on-site visit. This response will be recorded on the UBQ by the site staff. Subjects who did not return the keg will be retrained on product collection.

Patient Global Impression of Change – Menstrual Bleeding (PGIC-MB)

Subjects will use the PGIC-MB to assess the change in their severity of menstrual bleeding (from very much improved to very much worse) since initiation of study drug.

Columbia-Suicide Severity Rating Scale (C-SSRS)

The C-SSRS² is a systematically administered instrument developed to track suicidal adverse events across a treatment study. The instrument is designed to assess suicidal behavior and ideation and to track and assess all suicidal events, as well as the lethality of attempts. Additional features assessed include frequency, duration, controllability, reason for ideation, and deterrents. Site staff will administer the Screening/Baseline C-SSRS questionnaire in Screening and on Day 1. During the Treatment Period, site staff will administer the C-SSRS Since Last Visit questionnaire at the time points specified in Section 2.2. The C-SSRS administered at the Day 1 Visit will serve as the Baseline for clinical assessment.

During Screening or at the Day 1 visit, prior to randomization, any subject noted to have suicidal ideation with plan within the last year, either via answering "yes" to question 4 and/or question 5 to the suicidal ideation portion of the C-SSRS, or via clinical interview, is not eligible for randomization. In addition, any subject noted to have history of any suicide attempts "ever" on C-SSRS or via clinical interview, is not eligible for randomization. If the subject expresses suicidal ideation or suicidal behavior on the C-SSRS or via clinical interview at any time during the study, the investigator should take appropriate action to protect the subject (including possible discontinuation from the study and referral for appropriate psychiatric care) and then notify the AbbVie TA MD.

3.8 Clinical Laboratory Tests

Laboratory samples will be assessed using a certified central laboratory selected for this study. The central laboratory will provide instructions regarding the collection (including any fasting requirements), processing, and shipping of samples. Blood draws should be performed after vital signs and 12-lead ECG recording are conducted at a visit.

In the event that the central laboratory cannot be used to test samples because of the COVID-19 pandemic, samples may be obtained at a local laboratory or by a home health care service. AbbVie should be notified.

All clinical laboratory samples will be shipped to the central laboratory, with the exception of the venous blood sample for alkaline hematin analysis, which will be sent to the alkaline hematin laboratory.

All screening laboratory results must be reviewed prior to randomization, including any repeated test results. Screening laboratory tests may be repeated one time prior to Day 1; however, results must satisfy entry criteria prior to randomization. Subjects will not be randomized on Day 1 if screening laboratory results do not meet entry criteria or are assessed as clinically significant by the investigator. The laboratory test results obtained prior to Day 1 will serve as the Baseline for clinical assessment.

The central laboratory will provide the laboratory results to the investigative site where they will be reviewed, signed, and dated by the investigator. The investigator will receive sponsor-defined alerts from the central laboratory. For any value outside of the reference range and/or sponsor-defined alerts, the investigator will review and indicate on the report if the result is clinically significant or not clinically significant. The investigator will evaluate clinically significant laboratory values per standard of care, which may include repeating the test to verify the out-of-range value. Clinically significant laboratory abnormalities after randomization may be documented as AEs if they require discontinuation or at the discretion of the investigator (see protocol).

Samples will be obtained for the laboratory tests listed in [Table 1](#) at the time points specified in [Section 2](#).

Table 1. Clinical Laboratory Tests

Clinical Laboratory Tests				
Hematology	Clinical Chemistry (After Minimum 8-Hour Fast)	Lipid Panel (After Minimum 8-Hour Fast)		
Hematocrit Hemoglobin Red blood cell (RBC) count White blood cell (WBC) count Neutrophils Bands (if indicated) Lymphocytes Monocytes Basophils (if indicated) Eosinophils (if indicated) Platelet count (estimate not acceptable) Mean cell volume of RBC (MCV) Mean corpuscular hemoglobin (MCH) Mean corpuscular hemoglobin concentration (MCHC)	Sodium Potassium Chloride Bicarbonate Blood urea nitrogen (BUN) Serum creatinine Glucose Calcium Total protein Albumin Total bilirubin Alanine aminotransferase Aspartate aminotransferase Alkaline phosphatase Screening only Serum iron Serum ferritin Total iron binding capacity (TIBC) Vitamin D	Low-density lipoprotein cholesterol (LDL-C) High-density lipoprotein cholesterol (HDL-C) Triglycerides Total cholesterol		
		Endocrine Panel (Screening Only)		
		Follicle-stimulating hormone (FSH) Reflexive thyroid-stimulating hormone (TSH)		
		Urinalysis	Pregnancy Test	Other Tests (Screening Only)
		Specific gravity Ketones Protein Blood Glucose pH	Serum pregnancy (only when urine pregnancy test is positive)	Hepatitis B surface antigen (HBsAg) Hepatitis C virus antibody (HCV Ab)

Clinical Chemistry/Lipid Panel

Clinical chemistry and lipid panel samples should be obtained in the morning following an overnight fast (minimum of 8 hours); however, there may be circumstances when the sample is obtained later in the day and/or not under fasting conditions. If the sample was obtained with less than 8 hours of fasting, the source documents and the lab requisition should be marked to indicate that the sample was obtained under nonfasting conditions.

Pregnancy Tests (Serum and Urine)

Urine pregnancy tests will be performed at the time points specified in Section 2, in all subjects regardless of sexual activity status or method of contraception, including subjects who are surgically sterilized.

The urine pregnancy test result on Day 1 must be reviewed and confirmed to be negative prior to randomization.

During treatment period, a positive urine pregnancy test result must be confirmed with a quantitative serum pregnancy test. Study drug must not be dispensed if the subject has a positive urine pregnancy test result at any visit during the Treatment Periods (including Day 1 result). The site will immediately inform the subject to discontinue study drug temporarily while the subject waits for the results of the serum pregnancy test. If a serum pregnancy test result is positive, the subject will be prematurely discontinued from the study drug. The site should instruct the subject to complete a Premature Discontinuation visit within 2 to 7 days of study drug discontinuation.

In the event that a subject or study personnel cannot come to the site for a study visit requiring a urine pregnancy test because of the COVID-19 pandemic, home pregnancy test kits may be provided to subjects to self-administer at home and report results to study site over the phone.

If the subject becomes pregnant at any time after randomization up through 30 days after the last dose of study drug, an ultrasound examination will be performed as early as possible during the first trimester of pregnancy to assess the gestational age and estimated date of delivery. Refer to Section 4.4 for instructions on reporting of a pregnancy to the sponsor and the required follow-up on the subject's fetus, pregnancy, and infant outcomes.

Urine Test for Gonorrhea and Chlamydia (Optional)

Gonorrhea and chlamydia testing can be ordered at the investigator's discretion to test for active gonorrhea or chlamydia before the endometrial biopsy is performed. These samples will be sent to the central laboratory for analysis. If the investigator determines that an abnormal test result can be treated, treatment will be outside of the protocol. Follow-up gonorrhea/chlamydia testing (per instructions from the central laboratory) can be performed after treatment at the investigator's discretion.

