4 INVESTIGATIONAL PLAN

4.1 Overall Study Design and Plan

This is a Phase 4, randomized, double-blind, 6-month placebo-controlled, parallel-group, multicenter study. Premenopausal women 18 to 51 years of age with uterine fibroids and HMB, as evidenced by MBL > 80 mL during 1 menses in Screening as measured by the alkaline hematin method, will be selected for this study. See [Section 5.1](#) for information regarding eligibility criteria.

Once eligibility is established during the Screening Period, eligible subjects will be randomly assigned in the double-blind period at the baseline visit to receive either elagolix 150 mg QD or placebo in a 2:1 ratio for 6 months. Following the double-blind Treatment Period, there will be a 1 month Post-

[figure not shown]
Treatment Follow-Up (PTFU) Period. The study will be conducted in approximately 45 sites in the US (including Puerto Rico).

Total study duration can be up to 9 months (Screening Period of approximately 1.5 to 2.5 months prior to Study Day 1 [Baseline]). The study consists of the following 4 study periods:

- Washout Period: up to 10 months prior to Screening (only applicable if subject is taking exclusionary medication at the time of consent); duration is based on the excluded medication (Table 1).
- Screening Period: approximately 1.5 to 2.5 months prior to Study Day 1 (Baseline). Screening-related procedures to assess for eligibility must be conducted within first 1.5- to 2.5-month duration. However, in the event the cycle or product collection is not complete within 2.5 months during the Screening Period, the Screening Period may be extended with prior approval from AbbVie therapeutic area medical director (TA MD) and would result in a longer duration of participation for the subject than outlined.
- Treatment Period: duration of 6 months (double-blind). For all subjects who meet eligibility criteria during the Screening Period, each subsequent visit during the Treatment Period should be scheduled based on the date of the Day 1 (randomization) visit.
- PTFU Period: One month following the last dose of study drug. All subjects are expected to enter the 1-month PTFU after completing Treatment Month 6 or once a subject prematurely discontinues from the treatment period.

The schematic of the study is shown in Figure 1. Further details regarding study procedures are located in Appendix F, Operations Manual.

Figure 1. Study M16-824 Schematic

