5.6 Follow-Up for Subject Withdrawal from Study

To minimize missing data for efficacy and safety assessments, subjects who prematurely discontinue study drug treatment should complete the procedures outlined for the Premature Discontinuation visit (PD visit) as soon as possible, preferably within 2 to 7 days of study drug discontinuation.

Subjects should be advised on the continued scientific importance of their PTFU data even if they discontinue treatment with study drug early. All subjects should have an onsite PTFU visit 30 days after study drug discontinuation to ensure all treatment-emergent AEs/serious adverse events (SAE) have been resolved.

All subjects who prematurely discontinue will enter the 1-month PTFU Period unless the subject decides to discontinue the study participation entirely (withdrawal of informed consent).

All attempts must be made to determine the date of the last study drug dose and the primary reason for discontinuation of study drug and/or study participation. The information will be recorded on the appropriate eCRF page. However, these procedures should not interfere with the initiation of any new treatments or therapeutic modalities that the investigator considers necessary to treat the subject's condition. Following discontinuation of study drug, the subject will be treated in accordance with the investigator's best clinical judgment, irrespective of whether or not the subject decides to continue participation in the study.

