Reasonable Possibility	After consideration of factors including timing of the event, biologic plausibility, clinical judgment, and potential alternative causes, there is sufficient evidence (information) to suggest a causal relationship.
No Reasonable Possibility	After consideration of factors including timing of the event, biologic plausibility, clinical judgment, and potential alternative causes, there is insufficient evidence (information) to suggest a causal relationship.

Pregnancy

While not an AE, pregnancy in a study subject must be reported to AbbVie within 1 working day of the sites being made aware of the pregnancy and study drug must be discontinued (Section 5.5). A positive urine pregnancy test result must be confirmed with a quantitative serum pregnancy test. If the subject has a positive serum pregnancy test during the Treatment Period, no additional study procedures will be conducted; however, an ultrasound examination will be performed (and read locally) as early as possible during the first trimester of pregnancy to assess the gestational age and document an intrauterine pregnancy.

Pregnancies identified during the Treatment Period, although not AEs, will be monitored for fetus, pregnancy, and infant outcomes. The pregnancy outcome of an elective or spontaneous abortion, stillbirth or congenital anomaly is considered an SAE and must be reported to AbbVie within 24 hours of the site's being made aware of the event. For live infant births, information on the health of the infant will be collected from the first post-delivery pediatrician visit and at 6 to 12 months after delivery.

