PRO	
 • C-SSRS Since Last Visit • UFS-QoL 	
 • UBQ (if no sanitary product is returned) • PGIC-MB
LAB	
 • Urine pregnancy test (if positive, perform a serum pregnancy test) 	
 • Draw venous blood sample (only if PD prior to Month 6 and a keg is returned)
CENTRAL LAB	
 • Central laboratory tests (hematology, chemistry, lipid panels, urinalysis) • Pharmacodynamic sample (serum estradiol) 	
 • Pharmacokinetic sample: Elagolix plasma concentration • Optional biomarker sample: whole blood (DNA/RNA/serum/plasma)
TREATMENT	
 • Drug accountability 	

NOTES: All subjects must enter Post-Treatment Follow-Up (PTFU) Period unless subject withdraws consent or becomes pregnant during the Treatment Period.

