3.11 Contraception Counseling/Dispense Contraceptives

The sponsor will train investigators and study staff on the importance of contraception in this clinical trial. The investigator or designated study staff will counsel subjects (excluding those who have had a bilateral tubal ligation or bilateral tubal occlusion) at every on-site visit throughout study participation on the importance of pregnancy prevention and the use of appropriate and effective methods of contraception.

Subjects must agree to use at least 2 forms of nonhormonal contraception (dual contraception) as indicated in the protocol. If a subject has used LNG-IUS at least 6 months prior to the Screening visit and that remains in place throughout the Treatment Period through the PTFU Month 1 visit, she is not required to use 2 forms of nonhormonal contraception.

In the event that a subject or study personnel cannot come to the site for dispensing of nonhormonal contraceptive supplies because of the COVID-19 pandemic, nonhormonal contraceptive supplies may be provided to subjects via alternative means.

The following measures will be taken to help ensure pregnancy prevention during the study.

1. The informed consent form will include an attestation requiring the subject to confirm in writing (via signature) her full awareness that the potential risks of study drug on the unborn child are unknown, and therefore, she must not get pregnant during the entire time of study participation, and that she agrees to consistently use protocol-required nonhormonal contraception throughout her study participation.
2. The investigator or designated study staff will counsel the subject that the study drug is not contraceptive, that ovulation may occur even though the study drug may have altered menstrual cycle patterns, and that fetal abnormalities have been reported in women who have received elagolix in clinical studies; however, it is unknown whether these abnormalities were the result of taking elagolix.

3. The sponsor will provide training materials to the sites for instructing subjects on the types of protocol-allowed contraception methods, their effectiveness, and proper use.
 - The sponsor will provide all investigative sites with a supply of materials to promote pregnancy prevention, including contraceptives (e.g., condoms and spermicides) to provide to subjects at no charge.

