4.4 Pregnancy

Pregnancy in a study subject must be reported to AbbVie within 1 working day after the site becomes aware of the pregnancy. Information regarding a pregnancy occurrence in a study subject and the outcome of the pregnancy will be collected for any study subject with a positive serum pregnancy test after receiving at least one dose of study drug through 30 days following the last dose of study drug. While awaiting serum pregnancy test results during the Treatment Period, study drug should be temporarily discontinued.

If the subject has a positive serum pregnancy test during the Treatment or within 30 days following last dose of study drug, no additional study procedures will be conducted. However, an ultrasound

examination will be performed (read locally) as early as possible during the first trimester of pregnancy to assess gestational age and document intrauterine pregnancy. The following information should be collected: fetal outcome (e.g., spontaneous or elective abortion, live infant, or still birth), date and mode of delivery, birth weight, birth length, gender, any congenital anomaly, and medically significant complications during pregnancy or labor or delivery. For live infant births, information on the health of the infant will be collected from the first post-delivery pediatrician visit and at 6 to 12 months after delivery.

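### After a confirmed on-treatment pregnancy, the plan's instructions on the Premature Discontinuation visit are not reconciled, and SAP 8.4 counts pregnancy-related absence of bleeding as success

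*Protocol*

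**What the plan says.** **Procedures after a positive serum test.** Operations Manual 3.8 (Pregnancy Tests) takes the woman off study drug and continues: "The site should instruct the subject to complete a Premature Discontinuation visit within 2 to 7 days of study drug discontinuation". Protocol 6.1 says: "If the subject has a positive serum pregnancy test during the Treatment Period, no additional study procedures will be conducted", and then adds an ultrasound. Operations Manual 4.4 covers a "positive serum pregnancy test during the Treatment or within 30 days following last dose of study drug, no additional study procedures will be conducted", again with an ultrasound and collection of pregnancy outcomes.

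**Follow-up period.** Protocol 4.1 says: "All subjects are expected to enter the 1-month PTFU after completing Treatment Month 6 or once a subject prematurely discontinues from the treatment period". Protocol 5.6 says: "All subjects who prematurely discontinue will enter the 1-month PTFU Period unless the subject decides to discontinue the study participation entirely", meaning withdrawal of consent. The note to the Premature Discontinuation (PD) visit in Operations Manual 2.2 is wider. It sends all subjects into post-treatment follow-up (PTFU) "unless subject withdraws consent or becomes pregnant during the Treatment Period".

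**Bleeding endpoints.** SAP 8.4 defines amenorrhea at the Final Month as no bleeding or spotting days in the last 28 days up to the last dose. Suppression of bleeding is the same but allows spotting. If there are no evaluable alkaline hematin data, a Uterine Bleeding Questionnaire (UBQ) report of no bleeding is enough. Operations Manual 3.7 describes the entry: "If the subject did not have uterine bleeding or spotting the site staff will indicate" No. Both analyses need at least 38 days on drug. In the incidence summary, amenorrhea is carried forward after discontinuation whatever the reason.

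**Primary endpoint.** SAP 8.3.1 forces non-response for two discontinuation reasons only: lack of efficacy, and need for surgery or an invasive procedure for fibroids. Pregnancy is handled in SAP 9.7 by listings and an annualized rate.

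**The concern.** Missed menses is an expected sign of pregnancy, and the protocol does not present elagolix as preventing pregnancy. Operations Manual 3.11 has sites tell women that "the study drug is not contraceptive, that ovulation may occur even though the study drug may have altered menstrual cycle patterns". Absence of bleeding caused by pregnancy is therefore not a treatment benefit. Yet SAP 8.4 scores it as one, in endpoints compared between arms by the Miettinen-Nurminen method.

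The schedule tests for pregnancy at every monthly visit, so the event is foreseen; only its analysis is not. With 48 women, one case is visible in a percentage. If the rule is chosen after a case appears, the choice could favor either arm.

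Sites also have to work out for themselves whether the PD visit goes ahead. It is a full visit, with physical and gynecological examination, central laboratory tests, estradiol and drug samples, product return and questionnaires.

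**Working it through.** **1. The procedural texts side by side.**

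| Section | After a confirmed on-treatment pregnancy |
|---|---|
| Operations Manual 3.8 | Site should arrange a PD visit in 2 to 7 days |
| Protocol 5.6 | PD visit for all early discontinuers, then PTFU; only consent withdrawal exempt |
| Operations Manual 2.2, PD note | Exempt from PTFU; no exemption from the PD visit |
| Protocol 6.1, Operations Manual 4.4 | Nothing further except ultrasound and pregnancy follow-up |

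The first three rows fit a PD visit used as close-out. The last row, read literally, does not. For bleeding data this matters only when a pregnancy is found between monthly visits. At a monthly visit the products or the UBQ are collected anyway.

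**2. Who can be credited under SAP 8.4.** A month is 28 days and the visit window is ±5 days for Months 1 to 5.
- Month 1 visit: 28 ± 5 = Day 23 to 33, below 38 days, so no credit.
- Month 2 visit: 56 ± 5 = Day 51 to 61, above 38 days, so credit is possible, as at all later visits. That is 5 of the 6 scheduled monthly tests.

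**3. When the Final Month is free of bleeding.** The window runs from (last dose day − 27) to the last dose day. It is clear if the last dose day ≥ last bleeding day + 28. Assume 5 to 7 bleeding days. The last dose must then fall on cycle day 33 to 35 (5 + 28 to 7 + 28) or later. Eligibility allows cycles of 24 to 38 days.

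Assume also that the test turns positive when menses is due, that the next visit falls uniformly over the following 28 days, and that dosing stops at that visit.

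| Cycle | Menses due (cycle day) | Dosing needed past due date | Share with a clear window |
|---|---|---|---|
| 24 days | 25 | 8 to 10 days | (28−8)/28 = 71% to (28−10)/28 = 64% |
| 28 days | 29 | 4 to 6 days | (28−4)/28 = 86% to (28−6)/28 = 79% |
| 38 days | 39 | none (already met 4 to 6 days before) | 100% |

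Under these assumptions, most pregnancies first found at a Month 2 to 6 visit would be credited.

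**4. The planned sample size, as a check.** Inputs from Protocol 7.7: 10% v 55%, two-sided 0.05, 2:1 allocation. The normal approximation with continuity correction gives 16 placebo and 32 elagolix for 80% power, matching the plan. At 32:16, power is 91.1% without the correction and 86.5% by exact enumeration of Fisher's test. This concern does not affect the sample size.

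**5. Weight of one woman.** 1/32 = 3.1 points and 1/16 = 6.3 points. SAP 8.4 uses only women with 38 days on drug and a known status, so its denominators are no larger. For illustration, at the 28:14 assumed in SAP Appendix D, 1/28 = 3.6 and 1/14 = 7.1 points.

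**6. Effect on the primary test at about the planned rates.** Expected responders are 0.55 × 32 = 17.6 and 0.10 × 16 = 1.6. The Wald p comes from a logistic model with treatment only, without the baseline covariate or multiple imputation.

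| Elagolix v placebo | Wald p | Fisher p |
|---|---|---|
| 18/32 v 2/16 | 0.0086 | 0.0050 |
| 18/32 v 3/16 | 0.0191 | 0.0164 |
| 17/32 v 2/16 | 0.0131 | 0.0111 |
| 17/32 v 3/16 | 0.0297 | 0.0312 |

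Moving one woman in either arm, or one in each, leaves p below 0.05.

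**The case against.** Much can be said for the plan.

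- **The conflict is milder than it first looks.** A reader might infer that one section requires the PD visit and two forbid it. Operations Manual 3.8 says only that the site should instruct the woman, and Protocol 6.1 and Operations Manual 4.4 never name the visit. The PTFU exemption in the PD note presupposes that pregnant women have that visit. A workable order exists: stop drug, close out, no PTFU, ultrasound and outcome follow-up. This stands; what remains is that 6.1 and 4.4 do not say so.
- **The PTFU exemption exists.** The Operations Manual is Appendix F of the protocol, and Protocol 4.1 refers to it for procedures. A cross-reference from 5.6 is enough.
- **Monthly analyses are largely protected.** A reader might infer that every monthly rate is exposed. SAP 8.4 limits the monthly amenorrhea and suppression denominators to women on drug for the full window, and drops women who stopped in or before an interval from the observed blood-loss analysis. Only a window completed before detection is affected.
- **The 28-day window creates credit without pregnancy.** A woman with a 38-day cycle can have a clear window just before menses is due. This is true, but for 24- and 28-day cycles the credit arises only after menses is missed.
- **The setting limits the harm.** These are additional endpoints in a study now described as exploratory, contraception is generally required, and SAP 9.7 lists positive tests. This supports a low severity but does not remove the gap.

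**Conclusion.** The point holds and is minor. Two things are established from the text: the PD visit is not carved out of the no-further-procedures statements, and SAP 8.4 credits pregnancy-related absence of bleeding at the Final Month and in the carried-forward incidence summary.

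A reader might go further and infer that the primary endpoint is biased. The documents do not support that as a certainty. An observed 0 mL would count as response, and neither non-responder imputation nor the observed-case analysis would catch it. But the SAP does not say that a UBQ answer of No equals 0 mL for Final Month blood loss. If such a month is treated as missing, it is imputed. An early detection can also leave part of a menses in the window. Nor is pregnancy-outcome or serious adverse event reporting at risk.

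The size is at least 3.1 or 6.3 points per affected woman. The documents give no expected pregnancy rate, so the number affected is unknown and may be zero. The 64% to 100% range rests on the stated assumptions about bleeding days, detection and visit timing. The finding that the primary conclusion survives rests on results near the planned rates.

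**What to change.** 1. In Protocol 6.1 and Operations Manual 4.4, except the PD visit, completed as close-out, from the no-further-procedures statement for pregnancies confirmed during the Treatment Period. Refer Protocol 5.6 to the existing PTFU exemption in the PD visit note.
2. Before unblinding, add one rule to SAP 8.4. Bleeding data from the estimated conception date onward cannot establish amenorrhea or suppression of bleeding. The date comes from the ultrasound already required, or from the last bleeding day if the pregnancy is lost before ultrasound. A woman whose Final Month or completed monthly window includes that date counts as not achieving the endpoint, and no status is carried forward.
3. Leave the primary analysis unchanged and add one sensitivity analysis that counts such a woman as a non-responder.

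The cost is a few lines of text and one extra analysis, with no new procedure. The downsides are slight reliance on ultrasound dating, and that a woman whose bleeding the drug had truly suppressed before conception would be scored as not achieving the endpoint in that window.
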